4.2 Treatment Period

After the Randomization visit (Visit 3), patients will complete study visits at 1- to 4-week intervals according to the Study Plan (Table 1) until the end of the randomized treatment period (Visit 8, Week 16). During Weeks 6 to 16 of the double-blind treatment period of the trial, patients may be eligible for the addition of open-label rescue medication to their blinded treatment regimen in order to treat ongoing hyperglycemia, based upon established laboratory FPG values and repeat, confirmatory FPG criteria (Table 2).

Table 2 Criteria for Initiation of Rescue Therapy During the Randomized Treatment Period

Visit Period	Central Laboratory FPG
Week 6	FPG >270 mg/dL (15.0 mmol/L)
After Week 6 to Week 12 (excluding Week 12)	FPG >240 mg/dL (13.3 mmol/L)
After Week 12 to Week 16 (excluding Week 16)	FPG >200 mg/dL (11.1 mmol/L)

Abbreviation: FPG fasting plasma glucose.

Patients with a laboratory FPG value meeting the lack of glycemic control criterion at a pre-specified visit will be scheduled for a Follow-up Visit (within 3 to 5 days) to obtain a second laboratory FPG value and review the patient's glucose meter readings. If the repeat laboratory FPG value still meets the criterion, the patient must be rescued. Patients should continue receiving study medication while receiving rescue therapy. Patients who meet rescue criteria in the double-blind treatment period must first complete an OGTT and the Visit 8/End of Treatment procedures, including a glucose turnover study and DEXA scan, before receiving open-label rescue medication, to ensure that important trial endpoint measurements are collected. Rescued patients will be given open-label antidiabetic rescue medication in accordance with the approved product label in the applicable country at the discretion of the Investigator, in addition to their double-blinded study medication. Rescued patients will then continue in the double-blind treatment period according to their original visit schedule.

Following initiation of open-label rescue medication, rescued patients should have their glycemic response to the rescue medication evaluated by the Investigator. At the end of the study or at early termination, rescued patients should undergo a double tracer OGTT, glucose turnover study, and DEXA scan.

4.2.1 Treatment Period visits (Visits 4 to 7, Weeks 4, 8, 12, and 15)

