8.4 Outcome measures for analyses

The mean values will be compared between the treatment groups for the following measures:

1. Post-IP minus pre-IP EGP during glucose turnover study at Week 15.
2. Post-IP minus pre-IP EGP during glucose turnover study at Week 0 and the change from Week 0 to Week 15.
3. Pre-IP EGP during glucose turnover study at Week 15 and the change from Week 0 to Week 15.

4. Pre-glucose load EGP during the OGTT at Week 16 and the change from Week -1 to Week 16.
5. Change from Week -1 to Week 16 in post-glucose load EGP during the OGTT.
6. Change from Week -1 to Week 16 in Rd and Ra during OGTT.
7. Change from Week 0 to Week 16 in HbA1c.
8. Change from Week 0 to Week 15 in pre-IP plasma glucose during glucose turnover study.
9. Change from Week -1 to Week 16 in pre-glucose load FPG and post-glucose load PPG during the glucose turnover study.
10. Change from Week -1/0 to Week 15/16 in fasting plasma glucagon, C-peptide, and insulin during the glucose turnover study and OGTT.
11. Change from Week -1/0 to Week 15/16 in plasma glucagon, C-peptide, and insulin during the glucose turnover study and OGTT.
12. Change from Week 0 to Week 15 in post-IP minus pre-IP plasma glucagon, C-peptide, and insulin during the glucose turnover study.
13. Change from Week -1 to Week 16 in insulin secretion, beta cell function, and insulin sensitivity during OGTT.
14. Change in glucose oxidation and lipid oxidation during the baseline of the glucose turnover study, during the baseline of the OGTT, and post-glucose load during the OGTT.
15. Change in plasma ketones during the baseline of the glucose turnover study and OGTT.
16. Change from Week 0 to Week 15 in pre-IP, post-IP, and post-IP minus pre-IP in counterregulatory hormones during glucose turnover study.
17. Change from Week -2 to Week 16 in body weight and BMI; and percent body fat and fat distribution calculated from the DEXA scans.
18. Change from Week -1 to Week 16 in plasma GLP-1, GIP, and FFA during OGTT.
19. Change from Week -2 to Week 16 in FFA.
20. Change from Week 0 to Week 16 in waist to hip ratio, BP, and lipids.

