8.5 Methods for statistical analyses

Continuous variables will be presented with mean, median, 25th percentile, 75th percentile, standard deviation, minimum, maximum, and (if appropriate) the number of nonmissing observations. Categorical data will be displayed via absolute and relative frequencies for each category, including a category labeled as ‘missing’ when appropriate. The ‘missing’ category will not contribute to the denominators of relative frequencies.

All analyses will be done using values prior to rescue/intensification of treatment. Values collected after this time will be excluded from analyses. Sensitivity analyses may be conducted using all available data and including a time varying covariate that indicates rescue status.

The primary endpoint (EGP) will be tested for saxagliptin 5 mg/dapagliflozin 10 mg versus dapagliflozin 10 mg groups at the $\alpha=0.05$ level (2-sided). Other comparisons (contrasts) will be tested in an exploratory fashion at the $\alpha=0.05$ (2-sided) level. Therefore, no multiplicity control is required.

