8.5.2 Analysis of the secondary and exploratory variables

The continuous secondary endpoints will be analyzed using a repeated measures model when the endpoints are collected at visits in addition to Week 16. A longitudinal repeated measures analysis (using a MIXED model) for the change from baseline at Week 16, with terms for treatment group, baseline HbA1c subgroup ($\leq 8.5\%$ versus $> 8.5\%$), baseline treatment (metformin versus metformin/sulfonylurea) baseline value, time (each relevant visit), the interaction of treatment and time, and the interaction of baseline value and time in the model. Point estimates and 95% confidence intervals will be calculated for the adjusted mean changes within each treatment group as well as for the differences in adjusted mean changes between treatment groups.

The continuous secondary endpoints will be analyzed using an ANCOVA model like the primary endpoint when the endpoints are collected at baseline visit (Visit 3) and Week 16 only.

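### The plan does not say which model FPG gets or how rescued patients enter it; if FPG follows the primary ANCOVA, patients are selected on FPG and any true FPG difference shrinks toward zero

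*Combined protocol and SAP*

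**What the plan says.** **Trigger.** Section 4.2 of the protocol opens the rescue window at Week 6: "During Weeks 6 to 16 of the double-blind treatment period of the trial, patients may be eligible for the addition of open-label rescue medication". Table 2 gives the FPG thresholds. "Patients with a laboratory FPG value meeting the lack of glycemic control criterion at a pre-specified visit will be scheduled for a Follow-up Visit", where FPG is drawn a second time, and "If the repeat laboratory FPG value still meets the criterion, the patient must be rescued". Before rescue medication the patient must complete an OGTT and a glucose turnover study (sections 4.2 and 7.7.2; Table 1, footnote j). Rescued patients stay in the trial on blinded medication.

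**Data used.** Section 8.5: "All analyses will be done using values prior to rescue/intensification of treatment". Section 8.5.1 adds that a rescued subject does not contribute to the primary ANCOVA. The analysis in 8.5.4 that would use all data with a rescue covariate is optional.

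**FPG outcomes.** Section 8.4, item 8 is "Change from Week 0 to Week 15 in pre-IP plasma glucose during glucose turnover study". Item 9 is the pre-load OGTT glucose, Week -1 to Week 16. Table 1 also schedules a laboratory FPG at all eight visits, and section 5.1.2 lists FPG among the efficacy assessments. No item in 8.4 names the Week 4, 8 or 12 values.

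**Model.** Section 8.5.2: "The continuous secondary endpoints will be analyzed using a repeated measures model when the endpoints are collected at visits in addition to Week 16". Endpoints collected only at Visit 3 and Week 16 get an ANCOVA modelled on the primary one.

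**The concern.** A patient's later FPG values are set aside because that patient's earlier FPG was high. If FPG is then compared at Week 15 or 16 only among patients who were never rescued, the sample has been selected on the outcome. The arm with the weaker glucose lowering loses more of its high values, so the arms look more alike than they are.

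FPG matters here because section 1.1 argues that blocking the compensatory rise in EGP should lower FPG further. An attenuated FPG difference would weaken the clinical counterpart of the EGP result. Two sets of data already required by the protocol could prevent this: visit FPG before rescue, and the tracer tests done just before rescue. The plan does not say that either will be used for FPG.

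**Working it through.** **1. Which model does the text assign?**

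| 8.5.2 rule | Item 8 (Weeks 0 and 15) | Item 9 (Weeks -1 and 16) |
|---|---|---|
| Mixed model: also collected at other visits | Not if the endpoint is tracer-test glucose; yes if it is FPG in general | Same |
| ANCOVA: Visit 3 and Week 16 only | End value is Week 15, so no literal fit | Baseline is Visit 2, so no literal fit |

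Neither rule fits cleanly. With one baseline and one end value per tracer test, the ANCOVA is the likely default.

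**2. Which visits can select before Week 15?** Week 4 precedes the rescue window. Week 8 falls under the 240 mg/dL threshold. Week 12 is left out of both adjoining Table 2 rows: "After Week 6 to Week 12 (excluding Week 12") and "After Week 12 to Week 16 (excluding Week 16"). Table 1 nevertheless marks rescue dispensing at Visits 5, 6 and 7 (Weeks 8, 12 and 15). A Week 15 trigger arises at the visit where the Week 15 tracer value is itself drawn. Because the Week 12 rule is open, it is varied below.

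**3. Size.** The documents give no figure for any FPG contrast and no rescue rate, so there is no stated result to reproduce. They do give:

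- SGLT2 inhibition lowers FPG by about 30 mg/dL (section 1.1).
- Planned loss in the active arms is 10% for all causes, rescue included (section 8.2). That is 21 × 0.10 = 2.1, about two patients per arm.

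Assumed, not in the documents: baseline FPG mean 160, 180, 200 or 220 mg/dL; between-patient SD 40; SD of individual response 20; visit SD 18; combination effect −40 mg/dL. The true difference is then −40 − (−30) = −10 against dapagliflozin and −40 against placebo.

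Model: FPG at baseline = bᵢ + e; FPG on treatment = bᵢ + arm effect + rᵢ + e. Rescue occurs if both the visit value and its repeat exceed the threshold. There are 400,000 patients per arm. Attenuation = 1 − estimate/true.

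Combination minus dapagliflozin at Week 15 (true −10), range over the four baseline means:

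| Week 12 rule assumed | Rescued, dapagliflozin arm | ANCOVA without rescued | Attenuation | Mixed model, visit FPG to rescue | ANCOVA with pre-rescue tracer value |
|---|---|---|---|---|---|
| No trigger | 0.5–10.1% | −9.83 to −9.10 | 2–9% | −9.83 to −9.96 | −9.88 to −10.06 |
| >240 | 0.8–13.2% | −9.79 to −9.01 | 2–10% | −9.91 to −10.03 | −9.92 to −10.14 |
| >200 | 4.4–33.7% | −9.57 to −8.00 | 4–20% | −9.82 to −10.03 | −9.93 to −10.18 |
| >200, Week 15 triggers also dropped | 6.0–40.0% | −9.16 to −7.14 | 8–29% | −9.78 to −9.98 | −9.89 to −10.04 |

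Among all scenarios with dapagliflozin-arm rescue of about 10% or less, the estimate runs from −9.83 to −9.08: a bias of 10 − 9.83 = 0.17 to 10 − 9.08 = 0.92 mg/dL, or 2–9%.

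Against placebo (true −40), the ANCOVA without rescued patients gives −39.14 to −26.21 (2–34%) and the mixed model −39.92 to −38.65. The mixed model's remaining shortfall, at most 40 − 38.65 = 1.35 mg/dL (3%), arises because rescue also depends on the repeat value, which is not in the visit model.

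With no true difference (baseline mean 200, widest rule), the ANCOVA estimate is 0.04 mg/dL. Item 9 was not simulated separately; the same mechanism applies.

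**4. Scale against precision.** Under these SDs, the residual variance of Week 15 FPG given baseline is 20² + 18² + 40²·18²/(40² + 18²) = 400 + 324 + 269 = 993, an SD of 31.5. With 19 per arm the standard error is 31.5 × √(2/19) = 10.2 mg/dL. A bias of 0.92 is about 0.09 of that; the largest, 10 − 7.14 = 2.86, is about 0.28. The simulation error is 31.5 × √(2/400,000) = 0.07 mg/dL.

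**The case against.** The strongest reply is that the protocol already guards against this loss. It requires both tracer tests before rescue so that endpoint data exist, and section 8.5 admits values taken before rescue. Only the primary analysis expressly drops rescued patients. Using the pre-rescue tracer value leaves almost no bias in the table above. This stands as far as data collection goes. But items 8 and 9 name Week 15 and Week 16, no text says that an earlier pre-rescue value stands in for them, and the ANCOVA in 8.5.2 is defined by likeness to an analysis that leaves rescued patients out.

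A second reply is that 8.5.2 can be read to place FPG in the mixed model, since FPG is drawn at every visit. That reading is open, and under it the bias nearly disappears. It is not secured, because the outcomes are defined as tracer-test glucose.

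A third is that the effect is small. That is fair: under 1 mg/dL against dapagliflozin at the planned loss, well inside the standard error. Section 1.2 expects a low probability of rescue, and the placebo contrasts, where the loss is larger, are exploratory.

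A reader might infer more: that the plan has decided to ignore visit FPG, that rescued patients leave the trial, and that the FPG result will be materially biased. The documents do not support this. The model is unassigned rather than wrongly chosen, only later values are removed, and the larger attenuations need rescue well above the planned loss.

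**Conclusion.** The point holds conditionally. If FPG is analysed with an ANCOVA that leaves out rescued patients, the comparison is made in a sample selected on FPG and attenuates any true difference. Against dapagliflozin this is about 2–9%, under 1 mg/dL, when rescue in that arm is about 10% or less. It reached 20% when a 200 mg/dL threshold was applied at Week 12, and 29% when Week 15 triggers were dropped as well, with 40% rescued. Against placebo it is 2–34%. With no true effect it is about zero.

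These sizes rest on assumed FPG means, SDs and a combination effect that the documents do not give; the direction does not depend on those particular values. The point concerns a secondary outcome and does not touch the primary EGP comparison. It is worth correcting because the remedy is cheap and the present text leaves the choice of analysis open.

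**What to change.** 1. Add to section 8.4: change from Week 0 to Week 16 in visit FPG. Assign it by name to the 8.5.2 mixed model, using every pre-rescue visit value (Weeks 4, 8, 12, 15 and 16) of every patient in the full analysis set. Name the covariance structure, which 8.5.2 leaves open.
2. Keep items 8 and 9 as outcomes. State that fasting glucose from the mandatory pre-rescue turnover study and OGTT enters these analyses for rescued patients, so that they are not dropped. Correct item 9, which places the OGTT glucose in the turnover study, unlike section 2.2.
3. Reconcile the Table 2 intervals, which leave Week 12 uncovered, with the rescue dispensing marked at Week 12 in Table 1. How this is resolved is for the sponsor.

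**Cost.** One outcome line, one sentence on pre-rescue values and a model already written. No new sample or visit is needed, and step 1 and step 2 leave the rescue rule unchanged. The mixed model relies on missingness at random given observed FPG, which an FPG-based rescue rule largely supports. Items 8 and 9 would rely on carrying an earlier on-treatment value to Week 15 or 16. A single visit draw may also be noisier than tracer-test fasting values where several samples are averaged, which is a reason to keep both.

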3.3.1 Procedures for randomization

Patients who meet all study requirements based on inclusion and exclusion criteria will be randomized to 1 of 3 treatment groups (while continuing on metformin therapy) at Visit 3 (Randomization):

- saxagliptin 5 mg + dapagliflozin 10 mg;
- dapagliflozin 10 mg + placebo for saxagliptin;
- placebo for dapagliflozin + placebo for saxagliptin.

Stratification will be conducted according to baseline HbA1c level ($\leq 8.5\%$ or $>8.5\%$) and baseline therapy (metformin or metformin/sulfonylurea). Randomization codes will be assigned strictly sequentially within each stratum as patients become eligible for randomization. The HbA1c level collected at Visit 1 (Screening) will be used as the baseline HbA1c level for randomization purposes.

If a patient is discontinued from the study, his/her randomization or enrollment number will not be reused, and the patient will not be allowed to re-enter the study. Randomized patients who discontinue early from the study will be replaced to ensure adequate patient number as described in the sample size calculation.

If a randomization number is allocated incorrectly, no attempt should be made to remedy the error once study material has been dispensed. The patient will continue with the allocated number and study material. Subsequent patients will continue using the first unallocated randomization number in the original numbering sequence.

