Abbreviations: AE adverse event, β -hCG beta subunit of human chorionic gonadotropin, BP blood pressure, CrCl creatinine clearance, DEXA Dual Energy X-ray Absorption, ECG electrocardiogram, FFA free fatty acids, FPG fasting plasma glucose, GIP glucose-dependent insulinotropic polypeptide, GLP-1 glucagon-like peptide-1, HbA1c hemoglobin A1c, HDL high-density lipoprotein, HR heart rate, IgM immunoglobulin M, IP investigational product, LDL low-density lipoprotein, OGTT oral glucose tolerance test, R randomization, SMBG self-monitored blood glucose profile, T4 thyroxine, TSH thyroid stimulating hormone, WOCBP women of childbearing potential, IC = indirect calorimetry.

- ^a Early Termination procedures are to be completed for all patients who terminate the study or are rescued before Visit 8 (Week 16) of the Treatment Period. Discontinued patients should return to the study site and complete a glucose turnover study and all assessments required for Visit 8 (Week 16) 3 to 5 days later.
- ^b The glucose turnover study at Visit 3 should take place 5 to 14 days after OGTT at Visit 2. The Visit 7 glucose turnover study should take place approximately 10 days prior to OGTT at Visit 8.
- ^c Review of concomitant medications includes over the counter drugs and herbal/nutritional therapies.
- ^d 7-point SMBG should not be performed the day immediately before clinic visit 3 and 7.
- ^e Details for safety laboratory variables are shown in [Table 5](#).
- ^f Serum lipids include total-cholesterol, LDL-cholesterol, HDL-cholesterol, non-HDL cholesterol, and triglycerides.
- ^g Hepatitis panel includes hepatitis B viral antibody IgM, hepatitis B surface antigen, and hepatitis C virus antibody.
- ^h The double tracer OGTT will include blood draws for plasma glucose, plasma insulin, plasma C-peptide, plasma glucagon, plasma GLP-1, plasma GIP, plasma ³H-glucose, ¹⁴C-glucose specific activities (until Time 300 minutes) and urine will be collected.
- ⁱ The glucose turnover test will include blood draws for glucose, insulin, C-peptide, glucagon, cortisol, growth hormone, adrenaline, and noradrenaline; and ³H-glucose specific activities (until Time 300 minutes); and urine will be collected. Glucose turnover tests will include administration of IP at Time 0.

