- ^j Patients who are receiving rescue therapy or are early terminating: glucose turnover study will be performed 5 to 14 days prior to OGTT and Visit 8 assessments will also be completed prior to rescue. Glucose turnover study and Visit 8 procedures will be performed again at end of treatment for rescued patients.

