Prior to these visits, patients are to have fasted overnight (at least 10 hours). Patients are to refrain from alcohol intake and intense exercise 24 hours prior to each visit and recommend not to use tobacco/nicotine within 12 hours prior to each visit. Patients should delay administering their morning dose of metformin or metformin/sulfonylurea and study medication on the morning of the study site visits. Patients should bring their metformin or metformin/sulfonylurea and study medication with them to the study site and will self-administer study medication as directed by study site personnel.

The following will be performed during these visits:

- A brief physical assessment may be conducted at the Investigator's discretion.
- Body weight will be measured.
- Vital signs (reclining and standing systolic and diastolic BP and HR) will be assessed.
- Waist and hip circumference will be measured (Visits 4, 5, and 6).
- Concomitant medications (including over-the-counter and herbal/nutritional supplements) will be reviewed.
- Diet and exercise counselling will be provided (Visit 5 only).
- Study medication compliance will be reviewed.
- Patients will perform 7-point SMBG prior to visits.
- 7-point SMBG will be reviewed and recorded.
- Rescue medication will be dispensed (if needed, see [Table 2](#)).
- AEs will be reviewed.

- Urinary pregnancy test for all female patients (WOCBP only) will be performed.
- Blood samples will be collected **prior to administration of study medication** for the following assessments:
 - Chemistry and hematology (Visit 5 only)
 - Serum creatinine (calculated creatinine clearance; Cockcroft-Gault formula; Visit 5 only)
 - HbA1c
 - FPG and ketones
 - Fasting serum lipid concentrations (Visits 5 and 7 only)
 - Serum pregnancy test for all female patients (WOCBP only) if urine pregnancy test result is positive
 - Serum creatinine (estimated GFR)
 -
- Glucose turnover study will be performed. **Study medication will be ingested at the end of the 3-hour tracer equilibration period.**

Study site personnel will instruct patients to take IP and metformin (with food) after the study visit is complete.

4.2.2 End of Treatment Period Visit/Early Termination during Treatment Period or Rescue (Visit 8, Week 16)

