Prior to this visit, patients are to have fasted overnight (at least 10 hours). Patients are to refrain from alcohol intake and intense exercise 24 hours prior to each visit and recommend not to use tobacco/nicotine within 12 hours prior to each visit. Patients should delay administering the morning dose of metformin and study medication on the morning of the visit and bring metformin and study medication to the study site visit.

The following procedures will be conducted:

- A complete physical examination will be conducted.
- Body weight will be measured.
- BMI will be calculated.
- Vital signs (sitting systolic and diastolic BP and HR) will be assessed.
- Waist and hip circumference will be measured.
- 12-lead ECG will be performed.
- Concomitant medications (including over-the-counter and herbal/nutritional supplements) will be reviewed.

- Study medication compliance will be reviewed.
- Patient will perform 7-point SMBG prior to Visit 8.
- 7-point SMBG will be reviewed and recorded.
- Glucose meter and supplies will be collected.
- Unused study medication will be collected.
- AEs will be assessed.
- Urinary pregnancy test for all female patients (WOCBP only) will be performed.
- Blood samples will be collected **prior to administration of study medication** for the following assessments:
 - Chemistry and hematology
 - Serum creatinine (calculated creatinine clearance; Cockcroft-Gault formula)
 - HbA1c
 - FPG and ketones
 - Fasting serum lipid concentrations
 - FFA
 - Serum pregnancy test for all female patients (WOCBP only) if urine pregnancy test result is positive
 - Serum creatinine (estimated GFR)
 -
- Urine will be collected for urinalysis.
- Double tracer OGTT will be performed (approximately 10 days after glucose turnover study).
- DEXA scan will be performed or can be performed on a separate day.

If a patient is early discontinued or rescued, see visits 15 and 16 in Table for procedures.

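### Section 4.2.1 tells staff to have patients take IP after the visit with no exception for Visit 7, where IP has already been taken at Time 0 of the turnover study

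*Combined protocol and SAP*

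**What the plan says.** Section 4.2.1 covers Visits 4 to 7 (Weeks 4, 8, 12 and 15). Its opening paragraph has the patient hold the morning dose: "Patients should delay administering their morning dose of metformin or metformin/sulfonylurea and study medication on the morning of the study site visits". The last bullet of its procedure list is the glucose turnover study, with the instruction: "Study medication will be ingested at the end of the 3-hour tracer equilibration period". The sentence after the list reads: "Study site personnel will instruct patients to take IP and metformin (with food) after the study visit is complete". Neither the bullet nor the closing sentence names a visit.

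Table 1 schedules the turnover study at Visits 3 and 7 only, and its footnote i states: "Glucose turnover tests will include administration of IP at Time 0". Section 5.1.8 also places the end-of-treatment turnover study at Visit 7. It lets the patient go home after the 300-minute sample with a meal and metformin or metformin/sulfonylurea; IP is not mentioned at that point. Section 7.2 sets once-daily dosing and refers to a single daily dose on visit days, taken as site staff direct. Section 6.6 treats more than one tablet per day of either study drug as an overdose and requires the IRB to be told within 24 hours of staff becoming aware.

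**The concern.** The closing sentence of 4.2.1 is an operative dosing instruction, and it applies on its face to all four visits in the section. At Visit 7 two instructions about IP apply on the same day: one places the dose at the end of tracer equilibration, the other after the visit. Someone working down the visit list could carry out both.

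What is at stake is dosing accuracy and safety reporting on one day: a departure from the once-daily regimen, and an event that the protocol itself classes as an overdose. No efficacy result is at stake.

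**Working it through.** No sample size, power or alpha figure bears on this point. The check is a comparison of the text and a dose count.

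**Doses per visit day if 4.2.1 is followed literally, reading the turnover bullet with Table 1**

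| Visit | Turnover study (Table 1) | IP at Time 0 | IP after visit (4.2.1, closing sentence) | Tablets of each product |
|---|---|---|---|---|
| 4, 5, 6 | No | 0 | 1 | 0 + 1 = 1 |
| 7 | Yes | 1 | 1 | 1 + 1 = 2 |

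**Against the rest of the protocol, at Visit 7**

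- Section 7.2: once daily, so 1 tablet of each product. The literal count of 2 exceeds it by 1.
- Section 6.6: the limit is 1 tablet per day of either study drug. Since 2 > 1, the study-specific definition is met.
- Section 5.1.8: after Time 300, a meal and background therapy only. IP after the visit: 0, against 1 under 4.2.1.

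**Timing.** The first dose is at Time 0 and the last sample at Time 300. A post-visit dose therefore comes at least 300 − 0 = 300 minutes (5 hours) after the first, and after every sample that feeds the Week 15 post-IP minus pre-IP EGP difference. The endpoint cannot be altered by it. The sample size inputs in 8.2 (difference 0.39, SD 0.32, 19 per group) and the analysis model in 8.5.1 do not depend on it either.

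**Is the missing visit limit a matter of drafting style?** Elsewhere the same list does restrict items by visit: waist and hip circumference to Visits 4, 5 and 6, counselling to Visit 5, lipids to Visits 5 and 7. The parallel sections also avoid the problem. Section 4.1.3 (Visit 3, also a turnover day) has no post-visit IP instruction, and the closing sentence of 4.1.2 names background therapy only.

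**With the limit added:** Visits 4 to 6, 0 + 1 = 1; Visit 7, 1 + 0 = 1. All four visits then agree with 7.2.

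**The case against.** The strongest reply is that the documents already settle the matter. The opening of 4.2.1 has the patient hold one morning dose, and the two later sentences can be read as saying when that one dose is taken: at Time 0 if there is a turnover study, otherwise after the visit. Nothing mentions a second dose. Footnote i, 5.1.8 and 7.2 all point to one dose, and dosing is directed by trained staff at a single centre. This stands as evidence of intent, and it is why the point is minor. It does not correct the instruction: 7.2 defers to what staff direct, and 4.2.1 is the text that tells staff what to direct at that visit.

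A second reply is that 6.6 opens with a general definition under which an overdose must be both excessive and medically important, and no medical importance is shown for one extra dose. That is fair as regards harm. But 6.6 goes on to give a definition for this study based on tablet count alone, and two tablets meet it.

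A reader might also extend the point to turnover studies done before rescue or at early termination. The documents do not support that. Section 4.2.2 covers those patients and contains no instruction to take IP after the visit. Its pointer, "If a patient is early discontinued or rescued, see visits 15 and 16 in Table for procedures", leads to Table 1, which contains none either and whose footnote i places IP at Time 0.

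**Conclusion.** The point holds as a minor drafting defect: a stated dosing instruction that is wrong for one of the four visits it covers. Its size is one extra tablet of each product on the Visit 7 day, at least 300 minutes after the first, and only if staff apply the closing sentence literally. The conclusion assumes that Visit 7 runs as Table 1 and 5.1.8 describe, with IP at Time 0.

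Three stronger readings are tempting and are not supported:

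- That the plan intends two doses. The single held dose, footnote i, 5.1.8 and 7.2 all say otherwise.
- That the Week 15 EGP result is compromised. Every sample in that test precedes any post-visit dose.
- That a known number of patients would be overdosed or harmed. Counting the patients in the active arms gives only a ceiling. The documents give no basis for estimating how often a second dose would be taken, and show no harm from one.

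**What to change.** Make these edits in section 4.2.1:

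1. Mark the glucose turnover bullet *(Visit 7 only)*.
2. Begin the closing sentence with *Visits 4 to 6:* and extend its mention of metformin to *metformin or metformin/sulfonylurea*, to match the section's opening paragraph.
3. Add after it: *Visit 7: IP is taken once, at Time 0; after the 300-minute sample only a meal and metformin or metformin/sulfonylurea are given.*

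The cost is a few words in one section. Schedule, sample size, endpoint and analysis stay as they are, and 4.2.2 needs no matching change.
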